5.2 Screening potential participants in the ED

5.2.1 Overview

As stated in the protocol, in addition to clinic, potential participants will be identified in the ED.

In the ED, subjects will be identified by the PI or RC. The RC will ask the treating physician for permission to approach the patient. The RC will approach the patient in a private area conducive to private conversation (drawing the curtain in the ED). If the patient meets eligibility criteria (see 5.1.2) and expresses interest in participating in the study, the RC will take the patient's contact information (two phone numbers, address and email) to contact the patient at a later date to

discuss the study in greater detail and assess interest in participation. The patients contact information will be recorded in CRF 1 – Contact Information. The patient will be given information about the study (study brochure), and informed that there will be financial incentives for participating (metro-cards and gift cards at each visit).

5.2.2 Eligibility for screening ED patients

5.2.2.1 Inclusion criteria for screening

- Age 15 and older
- A history of SCD

5.2.2.2 Exclusion criteria for screening

- Unable to communicate
- Altered mental status
- Unstable vital signs
- The physician asks you not to approach the patient
- Pregnant

5.2.3 ED screening procedure

-
- The RC will monitor the tracking board for indicators that a patient has SCD (chief complaint contains the word 'sickle' or chief compliant contains the word 'crisis')
- Once a patient has been identified, the RC will ask the treating physician for permission to approach the patient.
- The RC approaches patient in an area conducive to private conversation (private room or curtain pulled).
- RC explains that they are collecting contact information for people interested in participating in a clinical trial of a treatment for SCD.
- If the patient expresses interest, RC records contact information on CRF 1 – Contact Info.
- Completed CRF's are stored in the IMPROVE folder in a locked cabinet in [name] office.
- The RC will enter CRF data into an encrypted Microsoft Access database and make weekly calls to prospective participants to arrange for an initial visit at the SCD clinic where the patient may be enrolled. In the event that the patient does not wish to follow in clinic but wants to participate in the study, a non-clinical visit in a private consultation room in the ED will be arranged.
- The RC will record de-identified information about each individual on CRF 10.
- The database will be destroyed when the study is complete.

5.3 Pre-screening and screening in clinic

5.3.1 Identification of eligible participants

When patients are greeted upon arrival to the SCD clinic, the RC will monitor the EPIC tracking board to identify patients who are above the age of 15 that have SCD. The RC will approach patients while they are in the waiting room to ask if they are interested in having a private discussion about a research study. Interested individuals will be brought to a private consultation area for screening and enrollment.

5.3.2 Eligibility

5.3.2.1 Inclusion criteria for randomization

- Age 15 and older
- Severe SCD phenotypes (Hb SS and S β thalassemia⁰)
- A positive response to cough/wheeze questions in CRF 3 – Screening Form.

5.3.2.2 Exclusion criteria for randomization

- Patient carries a physician diagnosis of asthma
- Patient is prescribed asthma medications
(Note: short acting beta agonists will **not** be considered as part of the list of “asthma medications” that are grounds for exclusion from the study. Classes of asthma medications that will still constitute grounds for exclusion include: inhaled steroids, long acting beta agonists, leukotriene modifying drugs, and IgE targeting monoclonal antibody therapies)
- Patient is currently having a painful crisis (as defined by validated pain diary questions)
- Patient has acute respiratory symptoms
- known hypersensitivity to milk proteins
- meets criteria for our operational diagnosis of asthma (CRF 3 – Screening Form) will also be excluded.
- More than 15 ED visits for pain over the preceding 12 months
- Admitted or discharged from the hospital for SCD pain within the last 7 days
- Patient is pregnant or planning to become pregnant during the duration of the study.

5.3.3 Procedure

If the participant expresses interest in participating in the study, the RC will bring the patient to a private area and ask questions in CRF 3 – Screening Form. Completed CRF 3 forms will be destroyed once the patient’s eligibility has been determined. If eligibility criteria are met on CRF 3 and the patient continues to express interest, the RC will then check EPIC for documentation that the patient has Hb SS or S β thalassemia⁰ and that the individual is not prescribed any asthma medications. If these criteria are met, the patient will be randomized.

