2.2.1 IMPROVE trial organizational chart

3.0 Study overview

We will conduct a randomized, double blind, placebo-controlled, feasibility study of mometasone furoate, an inhaled cortico-steroid (ICS), for 16 weeks in individuals with SCD and recurrent cough or wheezing who do not meet clinical criteria (derived specifically for individuals with SCD) for a diagnosis of asthma. Participants will be enrolled when they are pain free and have no acute respiratory symptoms. The sample size will be 45 participants, aged ≥ 15 , with 2:1 allocation of drug to placebo. Feasibility will be determined by the proportion of individuals successfully randomized who maintain good adherence and complete at least 30 pain diaries vs. the total number enrolled.

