5.3.4.3 Baseline data collection

After the participant has completed the informed consent process, CRF 3 will be completed again to ensure the patient's eligibility to be a part of the study. Then the senior RC will administer CRF 4 the baseline data collection form.

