Appendix 3 – HIMC SOPs

Supplement 2: Screening and eligibility form

(Affix Label Here) Participant ID: _____	Date Form Filled Out: _____ day month year	IMPROVE Inhaled Mometasone to Promote Reduction of Vaso-occlusive Events
--	--	--

Screening questionnaire to determine eligibility

Group 1

1. Does the participant's chest ever sound wheezy or whistling occasionally even without having a cold?
 Yes No
2. Has the participant ever had an attack of wheezing that has caused him/her to be short of breath?
 Yes No
3. Does this participant ever get attacks of wheezing after he/she has been playing hard or exercising?
 Yes No

Group 2

4. Has a doctor ever said the (BIOLOGICAL) mother of the participant had asthma?
 Yes No
5. Has a doctor ever said the (BIOLOGICAL) father of the participant had asthma?
 Yes No

Group 3

6. Has a doctor ever said that the participant has asthma?
 Yes No
7. Does the participant still have asthma?
 Yes No
8. Does the participant take any asthma medications?
 Yes No

Group 4

9. During the past 2 months, how often did the participant awaken from sleep because of cough or wheeze?
 Never
 Almost every night
 At least once a week but not nightly
 At least once a month but not weekly
 At least once but not monthly
10. During the past 2 months, how often did the participant cough or wheeze during or after exercise?
 Never
 Almost every night
 At least once a week but not nightly
 At least once a month but not weekly
 At least once but not monthly
11. During the past 2 months, how often did the participant cough or wheeze during the day unrelated to exercise?
 Never
 Almost every night
 At least once a week but not nightly
 At least once a month but not weekly
 At least once but not monthly

GROUP 5

12. Is the patient currently experiencing a sickle cell pain crisis?
 Yes
 No
13. Over the past 12 months how many ED or hospital visits did you have for sickle cell pain?
 0-5
 6-10
 11-15
 >15 (EXCLUDE)
14. Have you been admitted or discharged from the hospital in the past 7 days?
 Yes
 No
15. FEMALE PATIENTS ONLY: Is the patient Pregnant?
 Yes
 No

Inclusion/Exclusion Scheme:

Participants are eligible if they do not answer 'never' to all questions in group 4

Exclude Participants if

- a. They answer yes to all 3 questions in group 1
- b. They answer yes to 2 questions in group 1 and 1 or more questions in group 2
- c. They answer yes to questions 6 and 7 or questions 6 and 8

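### The written eligibility check has no step for three existing exclusions (milk-protein hypersensitivity, acute respiratory symptoms, planned pregnancy), so patients the protocol excludes could be randomized

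*Combined protocol and SAP*

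**What the plan says.** Section 5.3.2.2 lists nine exclusions for randomization. Three matter here: "Patient has acute respiratory symptoms"; "known hypersensitivity to milk proteins"; and "Patient is pregnant or planning to become pregnant during the duration of the study". The overview in section 3.0 repeats the respiratory condition.

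Section 5.3.3 sets out how eligibility is decided. The coordinator asks the CRF 3 questions. Then: "If eligibility criteria are met on CRF 3 and the patient continues to express interest, the RC will then check EPIC for documentation". The chart check covers two things, the sickle genotype and the absence of prescribed asthma medication. If both are satisfied, the patient is to be randomized.

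Section 5.3.4.3 adds a second look after consent: "CRF 3 will be completed again to ensure the patient's eligibility". It is the same form. CRF 3 is printed in Supplement 2, with 15 items in five groups, one inclusion rule, exclusion rules a to d, and a line for investigator approval.

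**The concern.** A procedure that decides eligibility should be able to detect every exclusion. If it cannot, it can return a patient as eligible whom the protocol means to keep out. Each of the three omissions has its own consequence.

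- **Milk-protein hypersensitivity.** The protocol itself treats this as a reason not to randomize, yet no written step asks about it before the inhaler is handed over. This is a safety matter.
- **Acute respiratory symptoms.** Exhaled nitric oxide (eNO) and spirometry are measured at entry, and change in eNO from entry to week 8 is a primary outcome of Aim 2. A baseline taken during an acute illness adds noise to the change score.
- **Planned pregnancy.** Participants who become pregnant are withdrawn. The primary feasibility outcome counts completion of follow-up, so this is attrition that a screening question could have avoided.

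**Working it through.** The plan gives no figure on this point, so the check sets the nine exclusions in 5.3.2.2 beside the CRF 3 items and the chart check in 5.3.3.

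| Exclusion in 5.3.2.2 | CRF 3 item or rule | Chart check |
|---|---|---|
| Physician diagnosis of asthma | Items 6–8, rule c | – |
| Asthma medication | Item 8, rule c | Yes |
| Current painful crisis | Item 12, rule d | – |
| Acute respiratory symptoms | None | – |
| Milk-protein hypersensitivity | None | – |
| Operational asthma diagnosis | Items 1–5, rules a and b | – |
| More than 15 ED visits for pain | Item 13, rule d | – |
| Hospital admission or discharge within 7 days | Item 14, rule d | – |
| Pregnant or planning pregnancy | Item 15, current pregnancy only | – |

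Tally: six have an item, one is covered in part, two are not covered (6 + 1 + 2 = 9).

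**Do the cough and wheeze items fill the respiratory gap?** No. Items 9 to 11 ask how often cough or wheeze occurred over the past two months, and any answer other than never qualifies the patient. Someone whose only cough comes from a current acute illness meets the inclusion rule because of that cough.

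**Does a later step catch the three?** The repeat in 5.3.4.3 uses the same form. The randomization program in 5.3.4.7 asks for hydroxyurea use, visits in the past year and the study number. The ED screening exclusions in 5.2.2.2 include pregnancy but none of the three.

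**Scale for eNO, by illustration.** Section 3.0 gives 45 participants at 2:1, so 30 on mometasone and 15 on placebo. Section 14.11 names 5 ppb as the difference detectable with 80% power. Assume that one participant's change is displaced by d ppb because baseline was taken during acute illness. The documents do not give d; the range used here is 5 to 30 ppb. The shift in the arm mean is d divided by the arm size.

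- Placebo: 5/15 = 0.33, 15/15 = 1.0, 30/15 = 2.0 ppb. The middle value is 1.0/5 = 20% of the design difference.
- Mometasone: 5/30 = 0.17, 15/30 = 0.5, 30/30 = 1.0 ppb.

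Randomization means that this has no expected direction. It is added variance.

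**Scale for feasibility.** One withdrawal for pregnancy lowers the feasibility proportion by 1/45 = 2.2 percentage points. With the 56 participants expected at baseline in Table 1 as the denominator, it is 1/56 = 1.8 points.

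**The case against.** The exclusions are binding whether or not a form prompts for them. Section 5.3.4.1 says that those consented and randomized are patients who meet the criteria, and CRF 3 ends with investigator approval. An investigator who knows 5.3.2.2 could catch all three. This stands in part: it rules out saying that such patients would be randomized, which a reader might infer from a literal reading of 5.3.3. But neither place names a question or source for the three items.

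Second, CRF 4 is completed before randomization and is not in the supplied text. Nor are the question-by-question guides or the other study documents that the manual mentions. Any of them might ask about allergy, current illness or pregnancy intention. This lowers confidence but does not remove the gap, since 5.3.3 does not make CRF 4 part of the eligibility decision and 5.3.4.3 uses CRF 3 for the recheck.

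Third, pregnancy surveillance runs through the study (weeks 2, 4, 8, 12, 16 and 20). It detects pregnancies after enrollment and so does not replace the entry criterion.

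A reader might also infer that the painful-crisis exclusion is checked with the wrong question. Section 5.3.2.2 says "Patient is currently having a painful crisis (as defined by validated pain diary questions", while CRF 3 asks "Is the patient currently experiencing a sickle cell pain crisis". The diary is not in the supplied text, so nobody can say from these documents that the form's wording departs from it. Likewise, "Participants will be enrolled when they are pain free and have no acute respiratory symptoms" is overview wording. Its difference from not being in crisis is minor and is not part of this point.

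**Conclusion.** The gap is real. Two of nine exclusions have no check in the written procedure, and a third is checked only for current pregnancy. Patients the protocol excludes could therefore be randomized.

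The number affected cannot be derived. The eNO figures rest on an assumed displacement and show scale only; they are not an estimate of bias. The conclusion assumes that CRF 3 as printed is the form in use and that no unseen document adds a required check before randomization.

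A missed exclusion would also be hard to find afterwards. Section 5.3.3 has completed screening forms destroyed once eligibility is settled, and a retained copy would hold no answer on these three items.

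**What to change.** Reconcile 5.3.2.2, 5.3.3 and CRF 3.

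- Add to CRF 3 one item for each of the three existing criteria: known milk-protein hypersensitivity, current acute respiratory symptoms, and planned pregnancy during the study. Make each an exclusion on its own, listed separately. Rule d as printed joins its conditions with the word and, so adding to it could be read as requiring all of them.
- Alternatively, name another documented check that is made before randomization and covers the three.
- Amend 5.3.3 so that randomization requires every exclusion in 5.3.2.2 to have been checked.

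This creates no new criterion. The cost is three short questions per screened patient and the IRB modification that section 13.3 requires for any CRF change. It may turn away a few patients whom the protocol already meant to exclude.

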5.3.4 Randomization and Enrollment

5.3.4.1 Overview

Individuals who meet inclusion/exclusion criteria will then be consented and randomized. The enrollment procedure is designed to maintain blinding of the participant, the PI and the senior RC. One RC will be unblinded (RC2) for purposes of introducing the study medication, training in proper use of the medication and refilling medication if the participant loses their medication.

5.3.4.2 Informed consent

Since an informed consent is a document required by law, this standard will require significant attention to all steps as set forth by good clinical practices. To ensure that patients’ rights are protected and that all study participants receive, read, have explanation of and sign an informed consent prior to enrolling in any study or protocol, the following steps will be followed. The principal investigator or designee must:

1. Know all of the elements of informed consent
2. Explain to the patient/parent the importance of and reasons for obtaining informed consent
3. Provide the patient/parent a quiet, undisturbed area for him/her to read the informed consent.
4. If the patient/parent is unable to read, then read the consent to him/her slowly.
5. After the patient/parent completes the reading of the consent, provide adequate time for him/her to ask any study or consent related questions of the study doctor and or study nurse.

Manual of Operating Procedures

6. Document these questions and answers in the progress notes of the chart along with a notation that the consent was read and reviewed by the patient/parent, that the patient/parent was provided a signed copy, as well as the date and time the informed consent was signed..
7. The patient/parent should then sign and date the consent in all areas appropriate with **BLACK** ink only.
8. Witness the patient/parent signing the informed consent, then sign and date in the witness space of the consent.
9. Give the patient/parent a signed photocopy of the informed consent.
10. Retain the original signed informed consent document in the research chart with a copy in the patient's outpatient chart.
11. If the patient/parent must ever sign a revised/amended consent for this study, repeat this process. DO NOT dispose of any prior consent(s). They all remain a part of the record.

5.3.4.3 Baseline data collection

After the participant has completed the informed consent process, CRF 3 will be completed again to ensure the patient's eligibility to be a part of the study. Then the senior RC will administer CRF 4 the baseline data collection form.

5.3.4.4 Urine and serum collection and processing

The patient will then go to phlebotomy to have labs drawn as part of standard care for their visit. Research tubes will be supplied to the phlebotomist to be drawn in addition to standard care labs. A sterile cup will be provided for urine collection. Processing of samples will be done according to the following protocol. Samples are to be stored in the Annenberg building in [name]'s lab ([name]).

In clinic:

Collect blood in one gold top serum tube (~5mls blood), one paxgene tube (2.5ml blood), and two green top tubes (~5.5ml blood each). All samples will be sent for processing de-identified. The gold top tube is labeled with the date, patient ID and inverted 2x and stored in a portable ice chest for up to 6 hrs until transfer to lab for processing. The PAXgene tube blood will be labeled with by the study name, followed by the ID number starting with 7001 (and so on for consecutive participants) and V1 or V2 to designate the time point collected (V1 at baseline and V2 at 8 Weeks). The PAXgene will be drawn vertically to allow blood to flow into the tube to exactly 2.5ml and inverted X8-10 after collection. The green top tubes will be labeled in the same manner as the PAXgene tube and inverted X5 after collection. The PAXgene tube can be kept at room temperature for up to 6 hours before transport at end of clinic day. The green top tube can be kept at room temperature for up to 30 minutes before transport to HIMC ([name]) for processing by HIMC staff.

For urine, instruct patient to sample clean catch in cup. Cup will be sealed, labeled, bagged and stored in a portable ice chest until processed.

In lab:

Blood: Spin at 2000 RPM, 5 mins, and aliquot serum into 4 labeled cryovials. Store at -80°C.

Label as:

Date Patient ID

Serum (or Urine)

PI: [name], MD

Urine: Transfer to vacutainer to centrifuge as above.

Aliquot in labeled cryovials and store at -80.

Manual of Operating Procedures

(For HIMC SOP see appendix)

5.3.4.5 Pulmonary Function Testing

Steps for PFT Testing

Summary: Calibrate the device before testing on patients for the day.

1. Calibration – typically once a day

- a. Go to Calibration
- b. Run QC Spirometry
 - i. Connect the 3-L syringe to the blue adaptor tube. Connect the other end of the blue tube to the narrower side of the mouthpiece, which then connects to the FVL. Make sure the syringe is closed. Click Done.
 - ii. The device will check for zero flow. Do not pump the syringe at this time.
 - iii. Following the instructions, pull the syringe to fill with air, then push at different flow rates:
 1. 2 times at the low flow rate target, at least 1 time at each of the higher flow rates
- c. Troubleshooting Failed ATS (failing QC)
 - i. Redo QC Spirometry.
 - ii. If failed again, click the red button at the lower left corner of the calibration home screen (diagnostics and device configuration).
 - iii. Go to Create New Span Factor → Span pneumotach F/V → With syringe connected, aim for targets
 - iv. Once ATS passed, click the red button (diagnostics and device configuration) and perform QC again.
 1. If QC still fails, then recalibrate by building a new table under diagnostics and device configuration.

2. Run Test

- a. Create a patient
 - i. Go to New Patient at the right of the Patients home screen.
 - ii. Fill in Identification and Information
 - iii. Save.
 - iv. For each test, fill in Biometrics, Smoking, Referral, etc.
 - v. Patients for the day can be found in the scroll down at the top of the program. Patients can also be searched under Find at the top or under Patients.
- b. Go to Run Test on the left or on the middle right of the patients home screen.
 - i. Enter Environmental Data (default values may be okay depending on study)
 - ii. Make sure patient's mouthpiece is attached to the FVL.
 - iii. Go to Start Pre Effort and allow device to verify zero flow. Make sure patient is not breathing into mouthpiece
 - iv. Ask patient to wear nose clip and to insert the mouthpiece, creating an airtight seal with the mouth and resting the tongue under the opening of the mouthpiece.
 - v. After at least two tidal waves of normal breathing, tell the patient to take a deep breath on the next inhale and to blast everything out as hard and fast as possible.
 - vi. Encourage the patient to continue pushing out air for at least 6 seconds. 8 seconds recommended. Watch the Forced Expiratory Time (FET) dial to countdown.
 - vii. Collect at least three good tests
- c. Administer 2 puffs albuterol via metered dose inhaler
- d. Repeat test using post bronchodilator fields

5.3.4.6 Measurement of Exhaled Nitric Oxide using NIOX Mino

1. Run Test

- a. Empty Lungs
- b. Inhale deeply through the disposable filter
- c. Make a seal with mouth on mouthpiece
- d. Exhale through the disposable filter for ten seconds or longer when machine beeps
- e. View the results on the screen

5.3.4.7 Randomization

Randomization will use an adaptive biased coin algorithm using the software program R as the user interface. After CRF 4 is complete the SRC will leave the room and the second RC (referred to as RC2 from this point forward) will enter to perform the randomization process.

RC2 will enter the room with the IMPROVE research cart and open the study laptop. RC2 will open R and load the randomization algorithm program. The program will prompt RC2 to enter a) whether or not the patient takes hydroxyurea and b) how many ED visits or hospital admissions for pain the patient has had over the preceding year c) the patients unique study identification number. The randomization algorithm will then notify RC2 which treatment arm the patient has been assigned to using a letter code (treatment arm A or B). Labeled study packets will be kept in the research cart and RC2 will hand the participant an appropriately labeled packet. At this time RC2 and the participant will open the packet together to review the study materials. The steps will be as follows:

1. Inhaler training – RC2 will train the participant in proper use of the inhaled medication including inhalation technique dosing intervals, what to do about missed doses.
2. Pain diary training – RC2 will train the participant regarding proper use of the pain diaries.
3. Contact information – RC2 will instruct the participant about how to contact study personnel in the event that the participant loses medication, has questions, suffers adverse events.

Once the training is complete, the participant will be instructed to put away their medication so that other study personnel do not see it. RC2 will leave the room.

The SRC will then enter the room and explain the schedule of financial incentives. The participant will be given a \$30 gift card and a \$11 metro card. A second follow up visit will be scheduled for 8 weeks from the current date. At this point the participant will be released and any other medical care will resume.

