4.3 Study medication

As already approved by the ISMMS research pharmacy, study medication will be stored in [name] office in a locked cabinet. Thermostat will be set at all times to maintain acceptable storage temperature (59-86 °F). Throughout the week, temperature and humidity (current readings as well as min and max for both) will be logged daily on the study medication temperature log sheet (CRF13) using a Fisher Scientific digital Traceable Thermometer/Clock/Humidity monitor. Over the weekend, min and max temperature and humidity will be logged on the Monday following. Min and max temperatures are stored after the memory is cleared (once each day). [name] packages, dispenses, and maintains accountability for all study medication is assisted by the unblinded RC in packaging and distribution.

Study packets for randomization will be made from sealable envelopes. Each packet will contain sufficient medication for 8 weeks (one 60-dose mometasone twisthaler or one placebo metered dose inhaler MDI). Packets containing active medication will include 'protocol orientation module A' (a document that has training and usage instructions for the mometasone twisthaler). Packets containing placebo will contain 'protocol orientation module B' (a document that has training and usage instructions for the placebo inhaler). Each packet will also include 60 pain diaries. Packets will then be sealed and labeled with a code. The code will indicate which treatment arm the packet corresponds to. The unblinded RC will have access to a master list that reveals the coding scheme, SRC and PI will not have access to this list.

In the event that [name] is not present during study recruitment/enrollment, licensed nurse practitioner [name] will be present to oversee dispensation of study drug or placebo.

5.1 Recruitment, screening and eligibility procedures:

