8.8 Financial Incentives/additional pain diaries

Once data collection is complete, the SRC will give the participant a second packet of pain diaries to complete over the subsequent 8 weeks. The SRC will also give the patient their financial incentives based on the number of diaries properly filled out as indicated by the schedule below (table 1).

Table 1
Timeline of financial incentives

	Visit 1 – Baseline Week 0	Visit 2 Week 8	Visit 3- end Week Obs	Observation† Week 20
Participants expected	56	50	45	45
Gift Card (\$30) -	X	X	X	X
Metro card (\$11) – travel costs	X	X	X	X
Gift card for completion of pain diaries	< 15 diaries – 0\$ 15-25 – 10\$ (50%) 26-50 – 20\$ (40%) 51-56 – 30\$ (10%)	< 15 diaries – 0\$ 15-25 – 30\$ (50%) 26-50 – 60\$ (40%) 51-56 – 90\$ (10%)	< 15 diaries – 0\$ 15-25 – 10\$ (50%) 26-50 – 20\$ (40%) 51-56 – 30\$ (10%)	< 15 diaries – 0\$ 15-25 – 10\$ (50%) 26-50 – 20\$ (40%) 51-56 – 30\$ (10%)

†Observational follow up period will continue for 4 weeks after study completion to measure adverse events, changes in pain and the proportion who choose to continue ICS.

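### The unblinded coordinator gives the baseline pain-diary training after learning the arm, an avoidable risk to the exploratory drug-versus-placebo diary comparisons

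*Combined protocol and SAP*

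**What the plan says.** Section 5.3.4.7 sets the order of the enrolment session. The SRC, who is blinded, completes CRF 4 and leaves. RC2 comes in and runs the algorithm: "The randomization algorithm will then notify RC2 which treatment arm the patient has been assigned to using a letter code". Next, "At this time RC2 and the participant will open the packet together to review the study materials". RC2 then trains on the inhaler, and as a second step "RC2 will train the participant regarding proper use of the pain diaries". RC2 leaves, and the SRC comes back to explain the incentives.

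Section 4.3 describes the packet. It holds "one 60-dose mometasone twisthaler or one placebo metered dose inhaler MDI", and "Each packet will also include 60 pain diaries". On the letter code, "The unblinded RC will have access to a master list that reveals the coding scheme"; the SRC and the principal investigator do not have that list.

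Section 5.3.4.1 gives the reason for unblinding RC2: "for purposes of introducing the study medication, training in proper use of the medication and refilling medication". Diary training is not mentioned there. At week 8 the handover of diaries belongs to blinded staff: "the SRC will give the participant a second packet of pain diaries" (8.8; 10.7 does the same at week 16). Sections 8.5 and 10.3 have RC2 complete the adherence forms. The 8.5 check includes a minimum diary count. Both sections say that a participant below the cut-off for doses or diaries is re-instructed, without saying by whom.

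**The concern.** The diary is a subjective, self-reported instrument. Under 14.7 it yields mean pain severity, pain days, crisis days and days of opiate use, and the pain measures are compared between mometasone and placebo. How a participant is taught to grade pain, or to recognise a crisis day, can affect what is written down. If the teacher knows the arm, emphasis or explanation may differ by arm without intent. Everyone randomized is trained in this way after allocation, so the trial has no group trained by blinded staff against which a difference could be checked.

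At stake is the credibility of the diary estimates that are meant to help choose an outcome for a definitive multi-center trial (14.3).

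**Working it through.** The point is procedural, so the main check sets the sections side by side. A short calculation then shows the scale on which a reporting shift would matter.

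**1. Does RC2 know the arm when diary training starts?** Yes, by two routes. The algorithm gives RC2 the letter code and RC2 can decode it from the master list (5.3.4.7, 4.3). Separately, the packet is already open, and a twisthaler or a metered dose inhaler shows the arm on sight (4.3).

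**2. Does the task need that knowledge?** No. Inhaler training must be specific to the device. Nothing in the diary step depends on the arm, and the diary paragraphs in Orientation Modules A and B are worded alike.

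**3. Is a blinded person available?** Yes. The SRC is in the room immediately before randomization and again immediately after RC2 leaves (5.3.4.7).

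**4. Which analyses are exposed?**

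| Outcome | Planned comparison | Exposed to arm-dependent diary coaching? |
|---|---|---|
| Diary pain measures (14.7) | mometasone vs placebo | Yes |
| Feasibility, including 30 diaries (14.2, 14.6) | ED vs clinic | Not as an arm contrast |
| eNO and sVCAM change (14.4) | mometasone vs placebo | No, they do not use the diary |

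**5. The plan's own figure.** Section 14.8 states power of 0.74, 0.77 and 0.80 for a 1-point difference in mean pain score at correlations r of 0.40, 0.30 and 0.20. It gives neither the SD nor alpha, so these values cannot be reproduced from the documents alone. Assume two-sided alpha 0.05 and 45 participants split 2:1 (3.0), that is 30 and 15. Then SE² = SD² × f(r) × (1/15 + 1/30) = SD² × f(r) × 0.1.

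- Taking f(r) = (1 + r)/2, the variance factor for the mean of two repeated measures, power 0.80 at r = 0.20 requires SE = 1/(1.960 + 0.842) = 0.357, hence SD = 0.357/√(0.6 × 0.1) = 1.46.
- That SD gives power 0.737 at r = 0.40 and 0.768 at r = 0.30, which agree with the stated 0.74 and 0.77. The value at r = 0.20 matches by construction.
- A change-score factor, 2(1 − r), and an ANCOVA factor, 1 − r², do not fit, because with them power rises with correlation.
- Under (1 + r)/2, an SD between 1.0 and 2.5 would put power at r = 0.20 between 0.98 and 0.37.

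**6. Illustration only.** Suppose there were no drug effect but diary reporting differed between arms by b points. The two-sided false-positive rate would be 1 − Φ(1.96 − b/0.357) + Φ(−1.96 − b/0.357).

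| Assumed b (points) | False-positive rate |
|---|---|
| 0 | 5.0% |
| 0.10 | 5.9% |
| 0.25 | 10.8% |
| 0.50 | 28.8% |

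The values of b are assumptions. Nothing in the documents indicates that any of them, or any value other than zero, would occur.

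**The case against.** Several counter-arguments are sound and limit the point.

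- Participants fill in the diaries themselves and RC2 does not score them. The written diary instruction is the same in both modules, and one payment schedule applies to both arms. These features make a large effect less likely. The shared paragraph, however, covers completion and not how to grade pain or crisis.
- A diary script may exist. Section 2.3 promises question-by-question guides for the CRFs, and the contents list a Pain Diary appendix that is not in the available text. The absence of a script therefore cannot be claimed.
- A reader might infer that 5.3.4.1 and 5.3.4.7 contradict each other. They do not quite do so. Section 5.3.4.1 gives purposes and does not say that the list is complete, and RC2 has other tasks elsewhere: running the randomization, CRF 8 and CRF 9, and possibly CRF 7. What stands is that diary training goes beyond the stated reason for unblinding, so the two sections should be aligned.
- A reader might infer that the primary outcome is compromised because feasibility requires 30 diaries. Feasibility is a pooled proportion, and its planned comparison is by recruitment site. Coaching that differs by arm does not bias that contrast.
- The different devices, and Module A's use of the active product's brand name, may inform the participant directly. That route may well matter more than one training step. It is a separate matter and gives no reason to leave an easily removed exposure in place.

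**Conclusion.** The point holds as an avoidable risk of bias. RC2 certainly knows the arm when teaching the diary, the task does not require it, and a blinded colleague is at hand. The endpoints affected are the diary comparisons of mometasone with placebo. The plan treats these as exploratory (14.7) and names no primary clinical outcome (14.3), although its Aim 1 power statement rests on them (14.8).

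The documents do not support saying that bias has occurred, that it has a particular size, or that it reaches the feasibility comparison or the eNO and sVCAM outcomes. The false-positive figures are conditional on assumed shifts, on two-sided alpha 0.05 and on the standard error implied by the stated 80% power. In a feasibility study with exploratory diary endpoints this is a low-to-moderate priority, worth correcting because correction is cheap.

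**What to change.** 1. In 4.3, pack the diaries separately from the medication envelope.
2. In 5.3.4.7, delete the diary step from RC2's list. Have the blinded SRC hand over the diaries and give scripted diary training after CRF 4 and before randomization, when nobody yet knows the arm.
3. In 8.5 and 10.3, state that the SRC gives any diary re-instruction, from the same script, and limit RC2 to inhaler and dose-count tasks. Without this, unblinded diary coaching could resume at follow-up even after 5.3.4.7 is changed. The SRC already pays incentives by the number of diaries completed (8.8, 10.7), so the SRC can supply the diary count for CRF 8 and CRF 9.
4. Align 5.3.4.1 with the resulting list of RC2's duties.

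The cost is wording changes in these sections, a short script if none exists, minor repackaging and a few minutes of SRC time per participant. No extra staff or visits are needed.
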